1.1.3. Observational Efficacy Assessment *between the 2 groups*

- Change in average daytime/night-time ambulatory systolic BP at 3, 6 and 12 months post-procedure from pre-procedure (including P and B) compared between the 2 groups (RDN-Treatment group vs. Sham group).
- Change in average daytime/night-time ambulatory diastolic BP at 3, 6 and 12 months post-procedure from pre-procedure (including P and B) compared between the 2 groups (RDN-Treatment group vs. Sham group).
- Change in average daytime/night-time ambulatory heart rate at 3, 6 and 12 months post-procedure from pre-procedure (including P and B) compared between the 2 groups (RDN-Treatment group vs. Sham group).
- Change in average 24 hour ambulatory heart rate at 3, 6 and 12 months post-procedure from pre-procedure (including P and B) compared between the 2 groups (RDN-Treatment group vs. Sham group).
- Change in office heart rate at 3, 6 and 12 months post-procedure from pre-procedure (including P and B) compared between the 2 groups.
- Incidence of ambulatory systolic BP (daytime/24-h/night-time) reductions of ≥ 5 mmHg, ≥ 10 mmHg, and ≥ 15 mmHg at 3, 6 and 12 months post-procedure from pre-procedure (including P and B) compared between the 2 groups (RDN-Treatment group vs. Sham group).
- Percentage of subjects who are controlled in the absence of changes in hypertensive medication at 3, 6 and 12 months post-procedure compared between the 2 groups. (Four different criteria of "controlled" will be used: daytime ambulatory BP < 135/85 mmHg; night-time ambulatory BP < 120/75; 24-h ambulatory BP < 130/80 mmHg; office BP < 140/90 mmHg)
- Percentage of subjects who are controlled irrespective of any changes in hypertensive medication at 3, 6 and 12 months post-procedure compared between the 2 groups (Four different criteria of "controlled" will be used: daytime ambulatory BP < 135/85 mmHg; night-time ambulatory BP < 120/70; 24-h ambulatory BP < 130/80 mmHg; office BP < 140/90 mmHg).

- Change in office and 24 hour ambulatory pulse pressure at 3, 6 and 12 months post-procedure from pre-procedure (including P and B) compared between the 2 groups.
- Changes in percentages of dipper/non-dipper patterns at 3, 6 and 12 months post-procedure compared between the 2 groups (Criteria for non-dipping is less than 10% decrease of night time systolic ambulatory BP from daytime BP).
- Change in number of antihypertensive drugs at 3, 6 and 12 months post-procedure from pre-procedure (pre-procedure visit (week -1)) compared between the 2 groups.
- Change in drug burden index at 3, 6 and 12 months post-procedure compared from pre-procedure (pre-procedure visit (week -1)) between the 2 groups (RDN-Treatment group vs. Sham group).
- Change in antihypertensive load index at 3, 6 and 12 months post-procedure from pre-procedure (pre-procedure visit (week -1)) compared between the 2 groups (RDN-Treatment group vs. Sham group).
- Percentage of subjects requiring initiation of additional antihypertensive drug therapy between 3 and 6 months post-procedure compared between the 2 groups (RDN-Treatment group vs. Sham group).
- Change in following body fluid composition parameters measured by the Body Composition Monitor (BCM), Fresenius Medical Care at 3, 6 and 12 months post-procedure from pre-procedure (pre-procedure visit (week -1)) compared between the 2 groups (RDN-Treatment group vs. Sham group)
 - o Weight, height, BMI, Overhydration (OH), OH % of extra cellular water
- Change in following parameters at all ambulatory BP measurements (24 hours ambulatory values, ambulatory values- day time and ambulatory values- night time) derived from Mobilograph® examination at 3, 6 and 12 months post-procedure from (pre-procedure visit (week -1)) compared between the 2 groups (RDN-Treatment group vs. Sham group).
 - o Pulse pressure, central systolic pressure (zSys), central diastolic pressure (zDia), augmentation index at 75 beats per minute (AIx at 75 bpm), heart minute volume (HMV), peripheral resistance, reflexion coefficient, pulse wave velocity (PWV)

All the analyses with respect to the 24 hour ambulatory parameters or office blood pressure parameters described under 1.1.1, 1.1.2 and 1.1.3 will be performed by comparing the treatment values at 3, 6, and 12 months from the pre-procedure value (1. Pre-treatment value (**P**) = average of the pre-procedure visit (week -1) value and screening visit (week - 4) value, 2. Baseline value (**B**) = pre-procedure visit (week -1) value only) in the RDN group and the sham group, separately (paired analyses) and compared *between the 2 groups*.

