1.1.2. Secondary objectives

The secondary efficacy parameters of the study are (*between the 2 groups* - RDN-Treatment group vs. Sham group):

- Change in systolic 24-h ambulatory BP at 3 and 12 months post-procedure from pre-procedure (including P and B) compared between the 2 groups (RDN-Treatment group vs. Sham group).
- Change in diastolic 24-h ambulatory BP at 3, 6 and 12 months post-procedure from pre-procedure (including P and B) compared between the 2 groups (RDN-Treatment group vs. Sham group).
- Change in office systolic and diastolic BP at 3, 6 and 12 months post-procedure from pre-procedure (including P and B) compared between the 2 groups (RDN-Treatment group vs. Sham group).
- Change in home systolic and diastolic BP at 3, 6 and 12 months post-procedure from pre-procedure (including B only) compared between the 2 groups (RDN-Treatment group vs. Sham group).
- Responder rate in BP (systolic office BP ≥ 10 mmHg, or 24-h systolic ambulatory BP ≥ 5

mmHg) at 3, 6, and 12 months post-procedure from pre-procedure (including P and B) compared between the 2 groups (RDN-Treatment group vs. Sham group).

- Change in serum creatinine, cystatin C at all time points from pre-procedure (pre-procedure visit (week -1) value and screening visit (week -4)) compared between the 2 groups (RDN-Treatment group vs. Sham group).
- Change in eGFR (calculated based on CKD-epi formula) derived from serum creatinine at all time points from pre-procedure (pre-procedure visit (week -1) value and screening visit (week -4)) compared between the 2 groups (RDN-Treatment group vs. Sham group). [1]
- Change in eGFR derived from cystatin C at all time points from pre-procedure (pre-procedure visit (week -1) value and screening visit (week -4)) compared between the 2 groups (RDN-Treatment group vs. Sham group). [2, 3]
- Change in eGFR derived from creatinine/Cystatin-C formula at all time points from pre-procedure (pre-procedure visit (week -1) value and screening visit (week -4)) compared between the 2 groups (RDN-Treatment group vs. Sham group) [3]
- Change of the slope of eGFR (derived from creatinine; CKD-epi formula) after half year and one year post-procedure from pre-procedure (pre-procedure visit (week -1) value and screening visit (week -4) eGFR values) compared between the 2 groups (RDN-Treatment group vs. Sham group).

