- Change of the slope of eGFR (derived from creatinine; CKD-epi formula) after half year and at 1 year post-procedure from pre-procedure (pre-procedure visit (week -1) value and screening visit (week -4) eGFR values) compared to the historical slope the year before
- Change in proteinuria (per g urinary creatinine), albuminuria (per g urinary creatinine), urine sodium (per g urinary creatinine), urine potassium (per urinary creatinine), urine creatinine concentration at 3, 6 and 12 months post-procedure from pre-procedure (pre-procedure visit (week -1) value and screening visit (week -4)) compared between the 2 groups (RDN-Treatment group vs. Sham group). Win ratio analysis will be conducted, with the criteria 24h ambulatory systolic BP change > 5 mmHg, and office systolic BP change > 10 mmHg at 3, 6 and 12 months from pre-procedure (including P and B) in both groups (RDN-Treatment group vs. Sham group). [4]
- Win ratio analysis will be conducted, with the criteria 24h ambulatory systolic BP change > 5 mmHg, office systolic BP change > 10 mmHg, and decrease of medication number at 3, 6 and 12 months from pre-procedure (including P and B) in both groups (RDN-Treatment group vs. Sham group). [4]
- Win ratio analysis will be conducted, with the criteria 24h ambulatory systolic BP change > 5 mmHg, office systolic BP change > 10 mmHg, and any decrease of drug burden index in both groups at 3, 6 and 12 months from pre-procedure (including P and B) in both groups

(RDN-Treatment group vs. Sham group). [4]

- Win ratio analysis will be conducted, with the criteria 24h ambulatory systolic BP change > 5 mmHg, office systolic BP change > 10 mmHg, and any decrease of antihypertensive load index at 3, 6 and 12 months from pre-procedure (including P and B) in both groups (RDN-Treatment group vs. Sham group). [4]

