2.4. Analyses

Statistical analyses will be based on the basis of international guidelines (CPMP/ICH/363/96:E9). Due to the early stop of the study, only an exploratory and descriptive analysis takes place. Statistical methods used to compare groups for primary and secondary outcomes:

Efficacy: Change of systolic 24-h ambulatory BP at 6 months post-procedure (primary efficacy endpoint) compared between the RDN and sham group will be analyzed in a linear mixed model including the covariates that were significantly different between the groups at baseline. All secondary (see 1.1.2) and observational endpoints (1.1.3 and 1.1.4) are analyzed also via a modelling approach adjusting for potential imbalances in baseline characteristics. The type I error for the analysis of the primary endpoint is set at 5% (two-sided), all analyses of secondary endpoints have an exploratory character avoiding multiplicity issues in this trial.

In addition, a win ratio analysis will be conducted, with the criteria 24h ambulatory systolic BP change > 5 mmHg, office systolic BP change > 10 mmHg, and decrease of medication as defined by following 3 parameters (number of antihypertensive drugs, drug burden index and antihypertensive load index).

Analysis will be performed for the following populations:

1. Primary analysis is based on *the intention-to-treat* (ITT) population consisting of all randomized study subjects that are all either RDN treated or sham treated.
2. A secondary analysis will be done with a *modified ITT* population (mITT) in which participants with adherence violations will be excluded (sensitivity analyses).
3. A secondary analysis will be done with the *per protocol population* (PPP) in which study subjects with predefined protocol deviations (defined prior to unblinding of the data) are excluded.
4. A secondary analysis will be done with the modified *per protocol population* (mPPP) in which study subjects of the PPP with adherence violation are excluded.
5. A secondary analysis will be done with the safety population (SAF) in which all study subjects signing informed consent are included.

6. A secondary analysis will be done with those patients that are investigated by the Erlanger and Nürnberger center (CRC staff), with a total of N=20 randomized patients (Bavarian cohort)

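### Drugs added before the 6-month reading have no counterpart in the primary or responder analyses, and the win-ratio drug tiers credit only decreases, so the device effect at unchanged medication can be shifted in either direction

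*SAP*

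**What the plan says.** SAP section 1.1.1 sets the primary endpoint as the between-group comparison of change in 24-h systolic BP at 6 months. Section 1.1.3 lists, as an observational outcome, "Percentage of subjects requiring initiation of additional antihypertensive drug therapy between 3 and 6 months post-procedure compared between the 2 groups". That window closes at the primary reading.

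The medication conditions attached to the other outcomes are as follows.

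- **Primary (2.4, 2.9.4.1).** The mixed model adjusts for covariates that differ at baseline; the t-test is unadjusted. Neither refers to medication changed after the procedure.
- **Responder rate (1.1.2, 2.1).** "Responder rate in BP (systolic office BP ≥ 10 mmHg, or 24-h systolic ambulatory BP ≥ 5" mmHg, with no medication condition.
- **Win ratio without drugs (1.1.2).** "24h ambulatory systolic BP change > 5 mmHg, and office systolic BP change > 10 mmHg at 3, 6 and 12 months".
- **Win ratios with a drug tier (1.1.2).** "office systolic BP change > 10 mmHg, and decrease of medication number at 3, 6 and 12 months from pre-procedure"; "office systolic BP change > 10 mmHg, and any decrease of drug burden index in both groups"; "office systolic BP change > 10 mmHg, and any decrease of antihypertensive load index". Section 2.4 repeats the direction: "and decrease of medication as defined by following 3 parameters".
- **BP control (1.1.3).** Two versions are given: one requires unchanged antihypertensive medication, the other disregards changes.
- **Drug use (1.1.3).** Changes in drug number, drug burden index and antihypertensive load index are compared between groups at 3, 6 and 12 months.

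**The concern.** Section 1.1 states the purpose as showing that the catheter system lowers ambulatory BP. A drug started between months 3 and 6 also lowers the 6-month reading. A patient whose pressure falls because of that drug contributes to the mean change and may count as a responder in the arm to which he or she was randomised. The SAP addresses this for BP control by giving both versions, but not for the primary or responder outcomes.

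The win ratio is the analysis that combines pressure and drug use, and three of its four versions do so. Their drug tier can register a reduction but not an increase, although an increase is the event that section 1.1.3 expects often enough to count. Two patients who are tied on pressure, one with a drug added and one unchanged, stay tied.

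At stake is how the 6-month difference, the responder difference and the win ratios are read: as the effect of a strategy that includes whatever drugs were added, or as the effect of the device.

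**Working it through.** The SAP gives no effect size, SD, rate of drug addition or drug effect, so there is no figure to reproduce. All inputs below are assumptions. A fall in BP is counted as positive.

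**1. Mean difference at 6 months.** If the added drug lowers 24-h systolic BP by *e* in both arms, and proportions p_R (RDN) and p_S (sham) receive one:

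observed difference = device effect + (p_R − p_S) × *e*

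With an imbalance of 0.10 to 0.30 and *e* of 5 to 9 mmHg, the shift runs from 0.10 × 5 = 0.5 to 0.30 × 9 = 2.7 mmHg. It is a dilution if sham has the excess, an inflation if RDN has it, and zero if p_R = p_S.

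Example with a device effect of 5 mmHg and *e* = 8:

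- 10% RDN / 30% sham: 5 − 0.20 × 8 = 3.4 mmHg
- 20% / 20%: 5.0 mmHg
- 30% / 10%: 5 + 0.20 × 8 = 6.6 mmHg

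**2. Responder rate, ambulatory limb only (fall of at least 5 mmHg).** Assume SD of change 12 mmHg and a sham mean fall of 2 mmHg. P(response) = Φ((mean fall − 5)/12).

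- No added drug: Φ(−0.25) = 0.40
- *e* = 5: Φ(0.17) = 0.57
- *e* = 9: Φ(0.50) = 0.69

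This is the shift for one patient who receives a drug. For the arm it is multiplied by the excess proportion: 0.10 × (0.566 − 0.401) = 1.6 points to 0.30 × (0.691 − 0.401) = 8.7 points. If RDN is the more-intensified arm (mean fall 2 + 5 = 7 mmHg, base rate 0.566), the rates with a drug are 0.720 and 0.820, and the shift is 0.10 × 0.154 = 1.5 to 0.30 × 0.254 = 7.6 points. Overall this is about 2 to 9 points. The planned definition also accepts an office fall of at least 10 mmHg, so these are not the planned responder rates themselves.

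**3. Between-arm responder difference, same limb, *e* = 8, device effect 5 mmHg.** With no additions it is 16.5 points.

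| Added drug, RDN / sham | BP-only | Added drug counted as non-response |
|---|---|---|
| 10% / 30% | 11.0 points | 22.9 points |
| 20% / 20% | 15.9 points | 13.2 points |
| 30% / 10% | 20.8 points | 3.5 points |

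The last column is (1 − p_R) × 0.566 − (1 − p_S) × 0.401. With unbalanced additions it lies on the other side of 16.5 from the BP-only figure; with balanced additions it lies further below 16.5.

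**4. Win ratio, simulated.** One run of 3,000 per arm, *e* = 8, drug decrease in 5% of each arm, correlated office BP with effects 1.3 times the ambulatory ones. The second decimal carries simulation error. The SAP does not say whether the BP criteria are pairwise differences or individual thresholds, so both readings are shown.

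| Added drug, RDN / sham | Pairwise: decrease-only | Pairwise: two-sided | Thresholds: decrease-only | Thresholds: two-sided |
|---|---|---|---|---|
| none | 1.79 | 1.79 | 1.85 | 1.85 |
| 10% / 30% | 1.49 | 1.55 | 1.55 | 1.73 |
| 30% / 10% | 2.07 | 1.99 | 2.18 | 1.83 |

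Most of the movement away from the no-addition value arises in the BP tiers. A two-sided drug tier recovers a small part of it on the pairwise reading and more on the threshold reading.

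**The case against.** The strongest reply is that nothing here is an error. The primary analysis is ITT, and comparing 6-month BP as measured, whatever drugs were added, is a legitimate treatment-policy contrast. That stands. The point concerns only a reading of the result as the device effect at unchanged medication; the SAP does not say which of the two it intends.

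A reader might infer that the plan is biased towards no effect. The document does not support this: it gives no rates of drug addition, the trial is double-blind, and an excess of additions in RDN would inflate the result instead.

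A reader might also infer that added drugs are invisible except in the control outcome that requires unchanged medication. That goes too far. Section 1.1.3 compares drug number and both indices between groups, the 3-month ambulatory contrast comes before the 3-to-6-month window, and the blinded review in section 2.6 could class some additions as major deviations. These let a reader see an imbalance, but they do not adjust the primary, responder or win-ratio results.

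The full win-ratio rules may sit in the cited method paper, which is not at hand. The statement that an increase ranks with no change therefore rests on the SAP's wording, which names a decrease in every place.

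Finally, all analyses are declared exploratory and descriptive. That limits the consequence to interpretation.

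**Conclusion.** The concern holds in a limited form. The SAP expects drug additions just before its primary reading, reports both medication versions for BP control but not for the primary or responder outcomes, and defines its win-ratio drug tiers in one direction only.

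Under the stated assumptions (10 to 30 point imbalance, 5 to 9 mmHg drug effect equal in both arms, SD 12 mmHg), the 6-month difference moves by 0.5 to 2.7 mmHg in either direction, and the ambulatory responder limb of the more-intensified arm by about 2 to 9 points. Balanced additions leave the mean difference unchanged and, in the example, move the responder difference only from 16.5 to 15.9 points.

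The rise from 40% to between 57% and 69% should not be read as a between-arm effect: it applies to a single patient given a drug, on one limb of the definition. Nor does the gap invalidate the ITT result. It is a cheap improvement to what can be concluded from that result.

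**What to change.** 1. **Win ratio.** In each version with a drug tier, compare the change from week −1 in drug number, burden index or load index, so that an increase loses to no change and no change loses to a decrease. Apply the same wording in sections 1.1.2, 2.1 and 2.4. This does not remove the drug effect from the BP tiers, which are decided first if the criteria are taken in the order listed.
2. **Primary.** Keep the as-observed 6-month result as primary and say that it is a treatment-policy comparison. Add one supportive analysis using the last ambulatory value before the first drug increase: week 12 if the increase came later, otherwise the pre-procedure value. Name the measure that defines an increase.
3. **Responders.** Beside the BP-only rate, and not in its place, report a version that also requires no drug increase, matching the pair already given for BP control.

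The cost is wording and programming. The flow sheet in section 1.3 has medication review at every visit and ambulatory BP at week 12, and section 2.7.2 requires records of medication changes.

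There are three downsides. More estimates have to be explained. The carried-back value may retain high readings in patients selected for intensification. The conditioned responder rate can overcorrect (22.9 or 3.5 points against 16.5 with no additions, in the example), which is why it should only supplement the BP-only rate. No rule on when drugs should be added is proposed.

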1.1.4. Procedure details in both groups (RDN group vs. sham group)

Procedure details in both groups (RDN group vs. sham group) will be presented as a table:

- Volume of contrast agent (cc)
- Minutes of exposure to fluoroscopy (mm:ss)
- Anesthesia Medications (Name, Dosage)
- No. of patients with accessory renal artery
- No pf patients with proximal artery branching
- Main Right Renal artery distal diameter (mean)
- Main Right Renal artery proximal diameter (mean)
- Main Right Renal artery length (mean)
- Main Left Renal artery distal diameter (mean)
- Main Left Renal artery proximal diameter (mean)
- Main Left Renal artery length (mean)

Renal denervation treatment details (RDN group only)

- Number of Left Main Renal Emissions
- Number of Right Main Renal Emissions
- Number of Left Renal BRANCH Emissions
- Number of Right Renal BRANCH Emissions
- Number of Left Renal Accessory Emissions
- Number of Right Renal Accessory Emissions
- Total Emissions (System Calculated)

1.1.5. Safety analysis

- Safety endpoints and adverse effects during 3, 6 and 12 months post-procedure compared between the 2 groups (RDN-Treatment group vs. Sham group).
- Listing of AE and ADE in original term provided for each patient (Solo-Population)
Listing of SAE, AESI, SADE in original term provided for each patient
Comparison of number / percentages of SAE, AE, AESI, escape rate between the 2 groups (RDN-Treatment group vs. Sham group)
- Increase of serum creatinine / eGFR (calculated based on CKD-epi) between visit 3a (week 0) and visit 3b, and visit 3a and visit 4 (week +3) between the 2 groups (RDN-Treatment group vs. Sham group) and in each group separately

Following events will be presented at all-time points post-procedure comparing 2 groups

All-cause mortality
New onset ESRD (eGFR<15 mL/min/m ² or need for renal replacement therapy)
Significant embolic event resulting in end-organ damage
Renal artery perforation or dissection requiring an invasive intervention
Major vascular complications requiring surgical repair, interventional procedure, thrombin injection, or blood transfusion
Hospitalization for hypertensive or hypotensive crisis
Hospitalization for major cardiovascular or hemodynamic related events
New onset stroke
New onset myocardial infarction
Suspicion of new onset renal artery stenosis by renal duplex ultrasound

Following AESIs will be presented as a table at all time points post-procedure comparing 2 groups

- All-cause mortality
- Hypertensive emergency resulting in hospitalization
- Hypotensive emergency resulting in hospitalization
- Hospitalization for heart failure
- Stroke, transient ischemic attack, cerebrovascular accident
- Acute myocardial infarction (STEMI/non-STEMI)
- Any coronary revascularization
- End stage renal disease, the need for permanent renal replacement therapy (i.e. the need for dialysis); doubling of plasma creatinine, eGFR <15ml/min/1.73m²
- Any renal artery complication requiring intervention (e.g. dissection; perforation)
- Major access site complications requiring intervention
- Significant embolic events resulting in end organ damage
- Procedure-related pain lasting for > 2 days
- Acute renal injury, defined as:

- Increase in serum/plasma creatinine to ≥ 1.5 times pre-procedure visit (week -1) or decrease of eGFR (derived from creatinine, CKD-epi) by 25% known to have occurred during 7 days post procedure or
- Urine volume < 0.5 ml/kg/h for 6 hours
- Significant ($> 50\%$) and severe ($> 70\%$) new onset renal stenosis as diagnosed by renal angiogram or CTA/MRA
- Need for renal artery angioplasty or stenting

In addition, these AESIs will also be reported as 1-month post-procedure event rates:

- Any renal artery complication requiring intervention (e.g. dissection; perforation)
- Major access site complications requiring intervention
- Significant embolic events resulting in end organ damage
- Procedure-related pain lasting for > 2 days
- Acute renal injury, defined as:
 - increase in serum/plasma creatinine to ≥ 1.5 times pre-procedure visit (week -1) or decrease of eGFR (derived from creatinine, CKD-epi) by 25% known to have occurred during 7 days post procedure or,
 - Urine volume < 0.5 ml/kg/h for 6 hours

Following major combined safety endpoint (incidence of any major adverse events (MAE) through the FU) at all time points post-procedure comparing 2 groups

- All-cause mortality
- eGFR < 15 ml/min/1.73m² or permanent need for renal replacement therapy
- Hospitalization for hypertensive crisis defined by office (attended) BP $\geq 180/110$ mmHg with clinical symptoms
- Clinical manifestation of hypertension associated target organ damage requiring hospitalization
- New renal artery stenosis $> 75\%$ as assessed by computer tomography (CT)/magnetic resonance angiography (MRA) or diagnosed/confirmed by renal angiogram
- Individual components of the combined endpoint above

